## 2. List of abbreviations

DMSB	Data Monitoring and Safety Board
DVT	Deep Venous Thrombosis
EC	Ethics Committee
e-CRF	Electronic Case Report Form
IRB	Institutional Review Board
LMWH	low-molecular-weight heparin
NOAC	New Oral Anti-Coagulant
PE	Pulmonary Embolism
VKA	Vitamin K Antagonist
VTE	Venous Thrombo-Embolism

#### 4. Synopsis

Title of the study	WHITE Study: WHIch decision after a first venous ThromboEmbolism? [Multicenter, multinational, investigators-initiated, observational, prospective study to evaluate the decisions taken by clinicians at the end of the maintenance treatment of subjects with a first-ever event of deep vein thrombosis of the lower limbs and/or pulmonary embolism, the relevant reasons, and the attending long-term outcomes]
Code of the study	WHITE Study
Version	Final Version
Date	20 September 2017
Design of the study	international, non-profit, multicenter, observational, prospective
Promoter of the study	Fondazione Arianna Anticoagulazione, Bologna (Italy)
International Coordinator of the study	[name]
Rationale	
Patients having experienced a first-ever episode of DVT of the lower limbs and/or PE, receive anticoagulation therapy for a period as recommended by international and/or local practice guidelines. When this recommended period expires, the attending physician has to decide whether to continue with anticoagulation, switch to anti-thrombotic of another class, or stop any prophylactic pharmacological treatment. Little is known as to which proportion of subjects is assigned to each alternative, whether this proportion is equivalent across different countries, different healthcare systems, and very little is known about the reasons guiding the physician's decision.
 
After the decision is taken, a number of validated data is available in the literature regarding the outcomes in subjects assigned to extended anticoagulation for up to one year, whereas little if any information is available for subjects receiving extended anticoagulation for more than one year, or assigned to alternative long-term treatment, or who stopped the treatment.
 
The Fondazione Arianna promotes this international, investigators-initiated, multicenter observational study, to collect data that may possibly answer the first question, and give substantial indications concerning the second question.

Main objective of the study	
This study includes two sections:
 
 
a] a transversal section, in which the primary objective will be evaluated;
 
b] a longitudinal section, in which the secondary objectives will be evaluated.
 
 
It is assumed that the distribution of the decision taken during the transversal section (primary objective) may influence the outcomes of the longitudinal section.
 
The primary objective of the study is the evaluation of the distribution of decisions and of the reasons guiding the physician's decision on the modality to manage the secondary prevention of venous thromboembolism (VTE) in patients treated for a first-ever episode of VTE, after the initial 3-12 months of anticoagulation therapy.
 
The secondary objective is the collection of data on the course of VTE recurrence, bleeding and death risk.

Endpoints of the study	
Primary endpoint:
 
The primary endpoint is the decision taken by the attending physician at the end of the period of maintenance anticoagulation (from the end of the 3rd month to the end 12th month) initiated after the index event (maintenance anticoagulation). The maintenance anticoagulant used may or may not be the same used in the acute phase of DVT (initial 7 days); for the objectives of this study, the acute treatment is not of interest. The primary endpoint will be evaluated at the visit performed at the end of the maintenance anticoagulation.
 
Secondary endpoints
 
The distribution of reasons guiding the physician's decision on the modality to manage the secondary prevention of VTE represents a secondary endpoint.
 
The other secondary endpoints encompass the frequency of thromboembolic complications, of bleeding complications, or death from any cause monitored during the follow-up.

Number of Countries	Nine: Portugal, Poland, Czech Republic, Slovakia, Rumania, Russia, Tunisia, China, Mexico
Number of Centers	Approximately from 5 to 20 Centers in each Country. Each center shall recruit not more than 40 subjects.
Number of patients	A minimum number of 3,200 subjects will be enrolled across all the countries participating to the study, split into: approximately 200 subjects in China approximately 350 subjects in Czechia; approximately 300 subjects in Mexico; approximately 900 subjects in Poland; approximately 350 subjects in Portugal; approximately 250 subjects in Romania; approximately 800 subjects in Russia; approximately 150 subjects in Slovakia; not less than 100 subjects in Tunisia.
Period of enrolment	Not more than eighteen months
Period of follow-up	Two years
Inclusion criteria	
 
a) subjects who provided a written informed consent and authorization for disclosure of protected health information;
 
b) male and female adult or elderly patients (<math>\geq 18</math> years at the time of signing the informed consent; no upper limit) of any ethnicity having had a first-ever event of provoked or unprovoked DVT of the lower limbs and/or PE given maintenance anticoagulants (NOACs, VKAs, or LMWHs) according to the local procedures (usually for 3 to 12 months) and to be re-evaluated to decide the treatment to be prescribed after such period;
 
c) for whom the center is in possession of all the data relevant to the index event;
 
d) having a permanent reference contact.
 

Exclusion criteria	
 
a) subjects <math>< 18</math> years old;
 
b) subjects unable or unwilling to issue the written informed consent;
 
c) subjects for whom the information relevant to the index event are incomplete or inaccessible to the Investigator;
 
d) subject in whom the index event was a DVT not of the lower limbs;
 
e) subjects with life expectancy of less than 2 years;
 
f) subjects participating in any other clinical study, regardless of its nature;
 
g) subjects considered, by the attending physician, unable to comply with the study procedures.
 

Study Procedures	
Enrollment and baseline visit:
 
 
1. the physician will assess the inclusion/exclusion criteria for entering the study and obtain the informed consent to confer the study data;
 
2. after obtaining the consent, the attending physician will record the diagnostic and prognostic information required in the CRF and inform the promoter of the recruitment of the patient;
 
3. the attending physician, based exclusively on the personal judgment and in accordance with the local procedures, will decide whether to continue with anticoagulation (NOACs or VKAs or LMWHs); or to switch to a long-term antithrombotic prophylaxis; or permanently discontinue the pharmacological prophylaxis. This decision generates three sub-populations with regards to the secondary prophylaxis of VTE: 
 
a] subjects receiving extended anticoagulation, with the same or another substance of the same class, at the same or lower dose as used in the maintenance treatment;
 
b] subjects receiving long-term antithrombotic non-anticoagulant prophylaxis;
 
c] subjects not receiving any long-term pharmacological prophylaxis.
 
 
 
4. the attending physician will record in the CRF the reasons guiding the decision taken;
 
5. the physician will instruct the subject on the procedures of the follow-up that should be the normal procedures in use at the Center, will provide a contact
 

	
reference and will obtain a contact reference.
 
Follow-up visits
 
The follow-up will be articulated as normally performed at the Center. The common follow-up procedures include a telephone contact every 3/6 months (4/8 in two years) and a direct interview at the center at least once a year (two in two years).
 
At each follow-up contact, by telephone or personal, information will be collected on:
 
 
survival at the time of contact;
 
hospitalizations occurred after the previous contact;
 
events of thromboembolic complication;
 
events of bleeding complication;
 
changes in the antithrombotic/anticoagulant therapy, if any was prescribed, including the institution of an antithrombotic/anticoagulant therapy if none had been prescribed;
 
other events that prevent the continuation of the planned follow-up.
 

	
Unplanned follow-up visits
 
It is possible, as usual during long-term monitoring of subjects, that visits are needed at the center upon request by the subject or based on the physician's decision. These unplanned visits, which will typically correspond to an event of recurrence or of bleeding, will record the same information as a standard follow-up visit. Performing an unplanned visit is not by itself considered a reason for terminating the study, unless the visit corresponds to one of the study endpoints (thromboembolic complications, bleeding complications, or other events preventing continuation of the follow-up).
 
End-of-study visit
 
The end-of-study information, collected at the last planned or unplanned contact with the subject, will only include the reason for terminating the observation on the individual subject.
 
The end-of-study visit will have to be completed for all subjects entered into the follow-up, and may occur:
 
 
at the end of the planned follow-up period;
 
when the investigator detects, or is informed of, the occurrence of a secondary endpoint (new thromboembolic event, major bleeding, clinically relevant non-major bleeding requiring a change of treatment; subject's death);
 
change (with the exception of dosage) or interruption of the prophylactic treatment assigned at recruitment (including not pharmacological treatment) by the attending physician or other physician;
 
subject's decision to stop the prescribed prophylaxis;
 
events occurred, which prevented the continuation of the follow-up (subjects lost to follow-up for any reason, including reporting to another center).
 

Sample size justification	
The primary endpoint is the decision taken by the attending physician at the end of the maintenance anticoagulation initiated after the index event. Three options are possible and in absence of other determinants, the null hypothesis is that the distribution of subjects by option is uniform. The analysis can therefore be performed with a goodness-of-fit test with 2 degrees of freedom. The alternative hypothesis is that at least one of the three choices is selected in a greater proportion than the other two. This analysis is performed once only at the end of recruitment.
 
With approximately 3,200 subjects, the study has 90% power to detect with 95% confidence a deviation from the uniform distribution, in case one of the options is selected in a proportion exceeding by 10% relative or more the proportion expected from the uniform distribution (i.e., in 36.3% or more of the subjects).
 
The study also has 80% power to detect with a two-tailed 97% confidence (accounting for interim analyses) a deviation of at least one of the sub-populations, by at least:
 
 
±1.23 recurrence events from the expected rate of 5 events per 100 subjects per year, and
 
±0.55 bleeding events/deaths from the expected rate of 1 event per 100 subjects per year.
 

Statistical-analytical plan	
Statistical considerations
 
The statistical analyses will be descriptive and exploratory. Given the nature of the

	
study, which is observational, it is not designed to confirm or reject predetermined hypotheses.
 
Populations
 
The analyses will be performed on the total sample monitored. Missing data will not be replaced.
 
Demographic, prognostic and descriptive variables
 
All variables will be summarized with the usual descriptive techniques: categorical variables as contingency table (absolute and relative frequency); continuous variables with sampling statistics: mean, standard deviation, median, minimum, maximum. Whenever appropriate the relevant 95% confidence interval will also be reported.
 
Primary endpoint
 
The primary endpoint will be analyzed at the completion of the recruitment. The proportion of choices made by the attending physician will be reported as proportion with confidence interval by level. The primary analysis will test by goodness-of-fit whether the choices were random or not. The impact of demographic and prognostic factors – including country – on the choice can be tested by chi square and/or logistic regression analysis.
 
Secondary endpoints
 
Frequency of thromboembolic complications and frequency of bleeding complications or death for any reason will be analyzed at the completion of each year of observation. The interim results will be used by the DMSB to decide on whether the observation has to continue or must be stopped. The final analysis will be adjusted for multiplicity using the nominal critical P value of 0.03.
 
Event rates will be reported at the available observations, stratified by sub-population, as proportion with the relevant confidence interval. Proportions will be compared if appropriate by chi square and/or as time to event by survival analysis.
 
Since clinically-relevant non-major bleeding may not be a reason for interrupting the follow-up, and minor bleeding are not a reason for interruption, it is possible that the number of bleeding events per subject can be submitted to analysis by Poisson regression.
 
The other secondary endpoint is the reason(s) justifying the choice analyzed as primary endpoint. These will be tabulated by choice and compared, if appropriate, by chi square test or by ordinal logistic regression. Unplanned post-hoc subgroup analyses may be performed if requested by the Steering Committee.
 
Other endpoints
 
Occurrence of hospitalization and changes of prophylactic therapy, including institution of a therapy in subjects who stopped any prophylactic treatment at recruitment; change of the prophylactic treatment assigned at recruitment, and interruption of the prophylactic treatment assigned at recruitment.
 
Hospitalizations will be analyzed as proportion of subjects with event, compared between sub-populations, if appropriate, by chi square or in case of an appreciable number of events, by Poisson regression.
 
Changes in therapy will be tabulated as absolute number and proportion stratified by sub-population and, if appropriate, analyzed by chi square and/or logistic regression. In addition, the reasons for study termination may be considered an endpoint. These will be tabulated by sub-population and compared, if appropriate, by chi square or ordinal logistic regression.
 
Safety observations
 
Adverse events will be handled by the attending physician according to the local procedures and, as in any observational study, will not be subject to statistical analysis. Only those events that resulted in the interruption of follow-up will be tabulated by sub-population and/or individual medication, without further statistical considerations.

--	--

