The secondary endpoints are the rate of thromboembolic complications and the combined rate of bleeding complications/death. To allow the DMSB (§ 11.3) to take appropriate decisions on the conduct of the study, these analyses will be performed at yearly intervals, i.e., when the last recruited subject has reached the end-of-year observation. There will therefore be 2 analyses (1 interim and one final), so that the final analysis will have to report as statistically relevant and deserving further investigations,  $P$ -values  $\leq 0.048$ .[8]

The interest of the study is to find whether any of the three constituted sub-populations – extended anticoagulation; long-term antithrombotic prophylaxis; no pharmacological prophylaxis (§ 8.1) – deviates from the expected risk, to an extent deserving investigation of the potential predictors of outcome.

From the literature [2, 3], the estimated annual risk of recurrence in the control group was approximately 5 events per 100 subject-years. The combined risk of bleeding or death was approximately 1 event per 100 subject-years.

Assuming that almost all recruited subjects will be monitored for at least one year, this survey has 80% power to detect with a two-tailed 95% confidence (after accounting for the interim analyses) a Cohen’s effect of the baseline decision taken on the follow-up outcomes, of 0.055 [9]. It can therefore identify as potentially relevant, deviations of at least one of the constituted sub-population from the anticipated recurrence rate of at least  $\pm 0.0123$  (3.77 or less, or 6.23 or more, events per 100 patients per year). Similarly, it has 80% power to detect with a two-tailed 95% confidence a deviation of at least one of the three constituted sub-populations from the anticipated bleeding/death rate of  $\pm 0.0055$  (0.45 or less, or 1.55 or more, events per 100 patients per year). [10]

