### 10.4.3 Secondary endpoints

The secondary endpoint analyzable at the completion of recruitment is the reason(s) justifying the choice analyzed in 10.4.2. These will be tabulated by choice and compared, if appropriate, by chi square test or by ordinal logistic regression. Unplanned *post-hoc* subgroup analyses may be performed if requested by the Steering Committee.

The other secondary endpoints include the frequency of thromboembolic complications and the frequency of bleeding complications or death for any reason. These will be analyzed at the completion of each year of observation (full year of observation of the last subject entered into the long-term follow-up). The interim results will be used by the DMSB to decide on whether the observation has to continue or must be stopped. The final analysis will be adjusted for multiplicity using the nominal critical P value of 0.048.

Event rates will be reported at the available observations as proportion, stratified by sub-population, with the relevant confidence interval. Deviations from the expected rate of events will be analyzed by chi square and/or time to event by survival analysis. If appropriate, subgroups will be analyzed with the Cox survival model. Impact of putative predictors as indicated by the Steering Committee will be analyzed by logistic regression and/or Cox proportional-risk model.

Since clinically-relevant non-major bleeding may not be a reason for interrupting the follow-up, and minor bleedings are not a reason for interruption, it is possible that the number of bleeding events per subject can be submitted to analysis by Poisson regression.

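### The synopsis and the body set different critical P values (0.03 and 0.048) for the same final analysis of the follow-up endpoints, yet claim 80% power for the same limits

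*Combined protocol and SAP*

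**What the plan says.** Two current parts of the document set the rule for the final analysis of thromboembolic complications and of bleeding or death.

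- **Synopsis (Section 4).** The statistical plan row states: "The final analysis will be adjusted for multiplicity using the nominal critical P value of 0.03". The sample size row claims 80% power at "two-tailed 97% confidence (accounting for interim analyses) a deviation of at least one of the sub-populations", with limits of plus or minus "1.23 recurrence events from the expected rate of 5 events per 100 subjects per year" and ±0.55 around 1 per 100 per year for bleeding or death.
- **Body.** Section 10.4.3 repeats the synopsis sentence with another number: "The final analysis will be adjusted for multiplicity using the nominal critical P value of 0.048". Section 10.2 and Section 11.3 also give 0.048, and Section 11.3 ties it to two analyses and an overall alpha of 0.05. On power, Section 10.2 says "this survey has 80% power to detect with a two-tailed 95% confidence (after accounting for the interim analyses", for a Cohen's "effect of the baseline decision taken on the follow-up outcomes, of 0.055". It converts this to recurrence limits of "3.77 or less, or 6.23 or more, events per 100 patients per year" and bleeding/death limits of 0.45 and 1.55. These are the synopsis limits.

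The document contains no rule on whether the synopsis or the body prevails. Section 5 says only that this is the final version.

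**The concern.** The difference is not between a superseded and a current text, since both are in force. It is also unlikely to be a single mistyped digit, because the two synopsis rows agree with each other (97% and 0.03) and the three body sections agree with each other.

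Two things are at stake:

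- **The reporting rule.** Section 10.2 uses the threshold to decide which results "the final analysis will have to report as statistically relevant and deserving further investigations". A final P between 0.03 and 0.048 qualifies under the body and fails under the synopsis. If this is left open, the choice could be made after the data are seen.
- **The power statement.** With the same sample size and the same limits, power must be lower at 0.03 than at 0.048 or 0.05. At most one of the two claims can be right if 80% is meant as the calculated value.

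**Working it through.** **Inputs.** Effect size w = 0.055, expected rates of 5 and 1 per 100 subject-years, and limits of ±0.0123 and ±0.0055 (Section 10.2). N = 3,200 (synopsis and Section 10.2). The country targets sum to 200 + 350 + 300 + 900 + 350 + 250 + 800 + 150 + 100 = 3,400, used as an alternative N.

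**Assumption.** Section 10.2 gives no degrees of freedom for this calculation. Two are assumed because there are three sub-populations and because this reproduces the stated power.

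**Step 1: reproduce the plan's figure.** Noncentrality = N × w² = 3,200 × 0.055² = 9.68. Power is the probability that a noncentral chi-square exceeds the critical value for the chosen alpha. On 2 df at alpha 0.05 it is 80.2%, which matches the stated 80%.

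The limits are reproduced by w × √(expected rate): 0.055 × √0.05 = 0.0123 and 0.055 × √0.01 = 0.0055. The plan does not state this formula; it is inferred from the match.

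**Step 2: change only alpha.**

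| N | df | alpha 0.05 | alpha 0.048 | alpha 0.03 |
|---|---|---|---|---|
| 3,200 | 2 | 80.2% | 79.7% | 73.9% |
| 3,400 | 2 | 82.7% | 82.2% | 76.9% |
| 3,200 | 1 | 87.5% | 87.2% | 82.7% |

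On 2 df, power at 0.03 falls short of 80% by 6.1 points at N = 3,200 and by 3.1 points at N = 3,400. At N = 3,200, the 0.05 and 0.03 columns differ by about 5 points on 1 df and about 6 on 2 df.

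**Step 3: what 80% power at 0.03 would require (2 df).**

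- With w = 0.055, N is about 3,640, which is 440 above 3,200 or 240 above 3,400.
- With N = 3,200, w is about 0.0587, giving 0.0587 × √0.05 = 0.0131 and 0.0587 × √0.01 = 0.0059, or ±1.31 and ±0.59 per 100 per year.
- With N = 3,400, w is about 0.0569, giving ±1.27 and ±0.57.

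**Step 4: is either threshold invalid in itself?** Assume two looks with half the information at the first; the plan does not give this fraction. A nominal 0.0294 at both looks then gives an overall two-sided alpha of 0.050, which is the Pocock boundary. The O'Brien-Fleming boundary has a final P of 0.0480 with an interim P of about 0.005. Each published value is therefore close to a recognised two-look design, but they are different designs. Section 10.2 cites a Lan-DeMets program without naming a spending function, and no interim level is given, so the text does not settle which was meant.

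**The case against.** The strongest objection concerns the size of the power shortfall.

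- **Degrees of freedom.** The 2 df stated in Section 10.2 belong to the primary endpoint. With 1 df, power at 0.03 is 82.7%, so a claim of at least 80% would hold at both levels. This is fair, but 1 df gives 87.5% at 0.05, which is not the figure the plan reports.
- **Conversion formula.** If limits are converted with √(p(1−p)) instead of √p, power at 0.03 on 2 df for ±1.23 is 76.4% at N = 3,200 and 79.3% at N = 3,400. For ±0.55 it is 74.4% and 77.3%. For recurrence the gap can thus shrink to under 1 point. However, that formula turns w = 0.055 into ±1.20, whereas √p returns the printed ±1.23.
- **Importance.** Section 10.1 calls the analyses descriptive and exploratory, the sample size rests on the primary endpoint, and a statistician working from Section 10 would apply 0.048.

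What stands is that the exact shortfall is uncertain and the practical effect is modest. None of this removes the conflict between the two thresholds. An exploratory label does not excuse it either, since Section 11.3 sets a significance rule in order to control alpha, and such a rule needs one value.

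**Conclusion.** The concern holds. The document gives two critical P values for one analysis and claims the same power for the same limits under both. The stated 80% fits 0.048 to 0.05 and does not fit 0.03, where it is missed by about 3 to 6 points depending on N. That range assumes a 2-df chi-square with w = 0.055; under the alternative conversion the gap for recurrence could be smaller. The thresholds disagree whichever assumption is used.

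This should be fixed, but it does not threaten the study. Only results with a final P between 0.03 and 0.048 would be classified differently, the endpoints are secondary, and the primary endpoint is tested once and is not affected.

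**What to change.** Reconcile the texts before the interim analysis.

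- **Simplest route.** In the synopsis, replace 0.03 with 0.048 in the statistical plan row, and replace the 97% confidence statement in the sample size row with the 95% overall wording of Section 10.2. Three body sections and the power figures already agree with this.
- **If 0.03 is intended.** Change one sentence in each of Sections 10.2, 10.4.3 and 11.3, bring the confidence statement in Section 10.2 into line, and restate the limits in both the synopsis and Section 10.2. The sponsor should recompute the limits with its own method; about ±1.31 and ±0.59 (N = 3,200, 2 df, inferred formula) is a guide only.
- **Optional clarification.** State that no significance claim is made at the interim, or give the interim level that goes with the chosen final level. At 50% information or more, an interim level of 0.0045 or stricter with a final 0.048, or 0.028 or stricter with a final 0.03, keeps overall alpha at or below 0.05.

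The cost is wording only, with no new data and no change in sample size. Under Sections 5 and 9.2 an amendment must go to the ethics committees before it is implemented, so the change could be bundled with another amendment, provided that happens before the interim analysis.

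### The follow-up question is deviation of a sub-population from a fixed expected rate, but the synopsis test reads as a between-group comparison and the 80% power figure mixes the two null hypotheses

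*Combined protocol and SAP*

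**What the plan says.** Section 10.2 states the question for the follow-up endpoints: "The interest of the study is to find whether any of the three constituted sub-populations" (extended anticoagulation, antithrombotic prophylaxis, none) "deviates from the expected risk, to an extent deserving investigation of the potential predictors of outcome". The expected risks are about 5 recurrences and about 1 bleeding/death event per 100 subject-years. The sample-size row of the synopsis puts its power claim in the same terms.

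On the analysis, two sections differ:

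- Synopsis, Statistical-analytical plan, Secondary endpoints: "Proportions will be compared if appropriate by chi square and/or as time to event by survival analysis". No expected rate is mentioned. The final critical P value is 0.03.
- Section 10.4.3: "Deviations from the expected rate of events will be analyzed by chi square and/or time to event by survival analysis". It also says "Event rates will be reported at the available observations as proportion, stratified by sub-population, with the relevant confidence interval". The final critical P value is 0.048.

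On power, 10.2 claims 80% with about 3,200 subjects for a Cohen's "effect of the baseline decision taken on the follow-up outcomes, of 0.055". From this it concludes that a deviation of at least one sub-population of ±0.0123 from the recurrence rate, or ±0.0055 from the bleeding/death rate, can be identified.

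**The concern.** Two null hypotheses are in play. One is that each sub-population has the expected rate; the other is that the three sub-populations have the same rate as each other. Three groups all at 7 per 100 satisfy the second and violate the first. A test of the second therefore cannot answer the question in 10.2 when the departure is shared.

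Section 10.4.3 addresses the right null but leaves the method open. It does not repeat the reference rate, give degrees of freedom or name a one-sample procedure. An ordinary log-rank test, which its survival-analysis option would allow, contains no external rate.

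The power statement then moves from an association between baseline decision and outcome to the distance of one group from a benchmark. A reader would take from it that a single sub-population 1.23 points away from 5 per 100 is found four times in five. The final analysis carries a critical P value, and the DMSB uses the interim results to decide whether observation continues, so the test and its sensitivity should be clear.

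**Working it through.** **Inputs.** N = 3,200, effect 0.055, rates 0.05 and 0.01, deviations 0.0123 and 0.0055 (10.2); critical P 0.048 (10.2, 10.4.3, 11.3) and 0.03 (synopsis). Assumed: one year of observation per subject, in line with 10.2's assumption of at least one year for almost all. Group shares are not given, so equal thirds (1,067/1,067/1,066) and 70/15/15% (2,240/480/480) were used.

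**1. Reproducing 0.055.** Noncentrality = N × w² = 3,200 × 0.055² = 9.68. Power from the noncentral chi-square:

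| df | w needed for 80%, P 0.05 | power at 0.055, P 0.05 | P 0.048 | P 0.03 |
|---|---|---|---|---|
| 1 | 0.0495 | 87.5% | 87.2% | 82.7% |
| 2 | 0.0549 | 80.2% | 79.7% | 73.9% |
| 3 | 0.0584 | 74.6% | 74.0% | 67.5% |

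Only 2 df reproduces the stated pair (0.055, 80%). That is the df of a test of equality among three groups. The documents do not state the df; this is an inference. At the synopsis's 97% confidence, 2 df gives about 74%, not 80%.

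**2. Reproducing the deviations.** 0.055 × √0.05 = 0.0123 and 0.055 × √0.01 = 0.0055. Both match, so they are distances from a fixed rate. Inverting: 3,200 × 0.0123² / 0.05 = 9.68. The full noncentrality is reached only if all 3,200 subjects deviate by 0.0123. In that case the three groups are equal and the between-group effect is zero.

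**3. Shift shared by all three groups** (simulation, 200,000 runs, equal groups, P 0.048):

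| true rate, all groups | between-group, 2 df | against fixed rate, 3 df | pooled against fixed rate, 1 df |
|---|---|---|---|
| 6.23% (expected 5%) | 4.9% | 75.9% | 86.3% |
| 3.77% (expected 5%) | 4.7% | 77.4% | 91.4% |
| 1.55% (expected 1%) | 4.8% | 73.6% | 80.7% |

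At P 0.03 the between-group test rejects 3.0% in the first row. The 70/15/15% split gives nearly the same figures.

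**4. Shift in one sub-population, the others at the expected rate.** Between groups, for 6.23%: the overall rate is (1,067 × 0.0623 + 2,133 × 0.05) / 3,200 = 0.0541. The noncentrality is [1,067 × (0.0623 − 0.0541)² + 2,133 × (0.05 − 0.0541)²] / (0.0541 × 0.9459) ≈ 2.10, so w = √(2.10/3,200) ≈ 0.026, under half of 0.055.

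The group's own one-sample test: expected events 1,067 × 0.05 = 53.4, SD √(53.35 × 0.95) = 7.12, and 1.977 × 7.12 = 14.1. It rejects upward from 68 events, while the mean at 6.23% is 1,067 × 0.0623 = 66.5. Exact binomial power is 44%. For 1%: expected 10.7, rejects upward from 18, mean at 1.55% is 16.5, power 39%.

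| one group moves, P 0.048 | between-group | 3 df, fixed rate | own one-sample test |
|---|---|---|---|
| 5% to 6.23%, n = 1,067 | 23% | 31–32% | 44% |
| 1% to 1.55%, n = 1,067 | 20% | 32% | 39% |
| 5% to 6.23%, n = 480 | 16% | 17% | 24% |
| 5% to 6.23%, n = 2,240 | 18% | 58% | 73% |

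**5. Sensitivity to observation time.** With two full years for everyone, one of three equal groups has 2,133 person-years and 106.7 expected recurrences. The Poisson test against that figure rejects upward from 128, with mean 2,133 × 0.0623 = 132.9, and power is about 68% (about 66% for 1 to 1.55 per 100). This is the most favourable case, because follow-up ends early at an event or a change of therapy.

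**The case against.** The strongest answer is that 10.4.3 already plans the analysis of deviations from the expected rate, and that both sections report each sub-population's rate with a confidence interval. This stands. A reader might infer from the synopsis sentence that the plan as a whole misses a shared shift about 95% of the time. The documents do not support that. The figure is the nominal level of a between-group test and applies only if that test is the sole one used; the analysis in 10.4.3 would have roughly 76% to 86% power for 6.23% against 5%, and the intervals would also help to reveal the shift.

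A reader might also point to the Cox model as a further use of the wrong null. That does not hold either. Section 10.4.3 assigns it to other purposes: "If appropriate, subgroups will be analyzed with the Cox survival model" and "Impact of putative predictors as indicated by the Steering Committee will be analyzed by logistic regression and/or Cox proportional-risk model". An external rate is not needed for those.

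The synopsis sentence names no comparator, and its own sample-size row refers to the expected rate. The between-group reading is therefore natural rather than explicit. Elsewhere in the same row the synopsis does spell out a comparison between sub-populations, for hospitalizations; that can be read as supporting either side.

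Finally, 10.1 calls the analyses descriptive and exploratory. This lowers the stakes, but it does not make the 80% figure correct.

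**Conclusion.** The point holds in a limited form. The synopsis and 10.4.3 describe the same final analysis differently, and only the 10.4.3 wording matches the stated question. Separately, the power statement joins a 2-df association effect over the whole sample to the deviation of one sub-population from a fixed rate, and that step does not follow. For one of three equal groups at the plan's own deviation, one-year power is about 23%, 31% or 44% for recurrence, and 20%, 32% or 39% for bleeding/death (between-group, 3-df fixed-rate and own one-sample test), not 80%.

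These figures rest on assumed group shares, one year per subject and P 0.048. A larger group or longer observation raises them, but none of the one-group cases examined reaches 80%. The 2 df is inferred from reproducing the plan's figure. The change is worth making, but given the exploratory status it does not threaten the study.

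**What to change.** 1. Reword the synopsis sentence to match 10.4.3. In both places name the test: observed against expected events in each sub-population (person-years times the stated reference rate), by a one-sample Poisson or one-sample log-rank test, reported with the rate and its confidence interval.
2. Label any between-group chi square or log-rank test as a separate exploratory question, not as evidence on deviation from the expected rate.
3. In the synopsis sample-size row and in 10.2, stop deriving the benchmark deviation from 0.055. Restate the power, or the detectable deviation, for one sub-population against the fixed rate over a range of group shares. As an illustration, the upward deviation d detectable with 80% power at P 0.048 over one year solves d = 1.977 × √(p0(1 − p0)/n) + 0.842 × √(p1(1 − p1)/n), with p1 = p0 + d. For p0 = 0.05 this gives about 0.030 at n = 480, 0.020 at n = 1,067 and 0.013 at n = 2,240, against the stated 0.0123.
4. Use one critical P value throughout when restating the figures, since the synopsis (0.03) and the body (0.048) now differ.

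The cost is wording in the synopsis, 10.2 and 10.4.3, a recalculated figure and one simple test. It needs no extra subjects or data. The downside is that the stated power will look less favourable.
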